4.3.2 Dosage, Administration, and Compliance

Nutropin AQ v1.1 will be provided to the patient and administered at a dose of up to 0.043 mg/kg/day (0.3 mg/kg/week). The dose may be adjusted at the Month 6 visit per investigator assessment for: 1) a change in body weight of at least ± 2 kg from baseline

Nutropin AQ (Somatropin [rDNA origin])—Genentech, Inc.

29/Protocol ML29543, Version 2

Clinical Study Report: Nutropin AQ (Somatropin)—Genentech, Inc. 378/CSR ML29543

OR 2) a change in IGF-1 level (if tested and the investigator deems a change in dose is clinically indicated).

The dose of Nutropin AQ v1.1 will be administered via SC injections by the patient or caregiver. Instructions and training on Nutropin AQ v1.1 administration with the NuSpin device will be provided by a trained study nurse coordinator.

Administration of the first dose of Nutropin AQ v1.1 (Day 1, baseline visit) should occur after the patient receives dosing administration instruction in the clinic and after the initial blood sample is drawn.

Blood samples scheduled after baseline (Months 1, 3, 6, 9, and Month 12 or early discontinuation) should be taken at least 12 hours after the last dose of Nutropin AQ v1.1 and prior to the next dose.

Missed doses or drug holidays are discouraged. Information on study treatment discontinuation and adverse events that may lead to discontinuation of treatment is provided in Sections 4.6.2 and 5.1.1, respectively.

The Nutropin AQ v1.1 solution contained within the NuSpin device contains a phenol preservative. The solution may be used for SC administration for 28 days after initial use when stored in the pen device at $2-8^{\circ}C/36-46^{\circ}F$ (under refrigeration). Avoid freezing the contents of the NuSpin device. The Nutropin AQ v1.1 contained within the device is light sensitive and should be protected from light. Store the NuSpin device refrigerated in a dark place when it is not in use. *Once study drug is assigned and dispensed to patients, they will be provided with containers for transport of the drug from the investigative sites to their homes for refrigerated storage.*

The solution in the device should be clear immediately after removal from the refrigerator. Allow the pen cartridge to come to room temperature and gently swirl. If the solution is cloudy, the contents must not be *administered and the affected pens should be returned to the site*.

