6.3.1 Primary Endpoint

The primary endpoint for this study is the proportion of patients who develop anti-GH antibodies after *initiating* treatment with Nutropin AQ v1.1.

6.3.2 Secondary Endpoints

The secondary endpoints for this study are as follows:

- Proportion of patients who exhibit growth attenuation (defined as initial growth response greater than pretreatment velocity followed by reduction in growth response to below the pretreatment velocity in the subsequent 6- to 12-month treatment period or reaching ≤2 cm per year)
 - Cross tabulation between growth attenuation status (i.e., with or without) and anti-GH antibody status (i.e., positive or negative) will be provided for any

Nutropin AQ (Somatropin [rDNA origin])—Genentech, Inc.

48/Protocol ML29543, Version 2

antibody and for neutralizing anti-GH antibody, respectively, at each visit. Similar tables will also be provided for patients who had at least one positive anti-GH antibody (anti-GH antibody and neutralizing antibody, respectively) at any follow-up visit against those who never developed antibody after treatment.

- Proportion of patients with neutralizing antibody among those who had positive anti-GH antibody
 - This analysis will be summarized by visit, as well as *cumulatively*, for patients who had detectible anti-GH antibody at any post-baseline visit, as well as those who *remained negative throughout the study*.
- Annualized 6- and 12-month growth velocities and height SDS will be summarized separately for patients who were anti-GH antibody-positive at any post-baseline follow-up visit and those who were anti-GH antibody-negative at all visits (including baseline). Graphic displays of the individual patient growth patterns along with the longitudinal antibody profile over the course of the study will be prepared. Patients who enter puberty during the study period will be included up to the last visit at which they were determined to be prepubertal.

Additional analyses deemed appropriate for assessing immunogenicity will be described in the Statistical Analysis Plan.

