4.4.1 Primary Outcomes Endpoint

The primary endpoint for this study is the proportion of patients who develop anti-GH antibodies (i.e., with positive anti-GH antibody screening assay result) after initiating treatment with Nutropin AQ v1.1.

Among all patients with at least one post-baseline screening assay result, the number and percentage of patients who have at least one positive anti-GH antibody screening assay result at any post-baseline visit will be presented. The Clopper-Pearson exact 95% Cls for the percentage will also be provided.

An anti-GH antibody screening assay result is considered positive if the titer is \geq 1.0 mg/L.

4.4.2 Secondary Outcomes Endpoints

The secondary endpoints for this study are as follows:

- Proportion of patients who exhibit growth attenuation is defined as
 - (1) initial growth response greater than pretreatment velocity followed by reduction in growth response to below the pretreatment velocity in the subsequent 6- to 12month treatment period

or

(2) reaching \leq 2 cm per year at any scheduled visit: Month 3, 6, 9, or 12

Please note that for criteria (1), the initial growth response occurs as early as Month 3 and growth attenuation status at post-baseline visit will be evaluated at Months 6, 9, or 12.

The growth response is based on the annualized growth velocity defined as (height - baseline height)/ (date of height assessment – date of baseline)*365.25 at any post-baseline visit.

Pretreatment growth velocity is defined as (Baseline height – last historical height) / (date of baseline – date of last historical height)*365.25

Growth attenuation status at post-baseline visit Tk (=Month 6, Month 9 or Month 12 for k=6, 9, or 12) will be classified as follows:

Yes: If growth velocity at Tk< pretreatment growth velocity and there is Tj < Tk with growth velocity at Tj > pre-treatment growth velocity, for j<k, and k=6, 9, or 12 or growth velocity \leq 2 cm per year at any scheduled visit: Month 3, 6, 9, or 12 **No:** Otherwise.

Nutropin AQ (Somatropin [rDNA origin])—Genentech, Inc. 9/Statistical Analysis Plan ML29543 • 2x2 cross tabulation (with frequencies and percentages) of growth attenuation status (yes or no) and anti-GH antibody status (positive or negative) will be provided for each antibody assay at each visit (Month 6, 9, and12).

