Similar tables of growth attenuation status (yes at any visit from Month 6 to Month 12) and anti-GH antibody status for those who had a positive antibody assay at any follow-up visit (negative at baseline) and those who remained negative throughout the study (including baseline) will also be provided.

- Proportion of patients with neutralizing anti-GH antibody (Nab positive) among those who had positive anti-GH antibody. This analysis will be summarized by visit, as well as cumulatively, for patients who had detectible anti-GH antibody (ATA) at any post baseline visit (with negative antibody assay at baseline), as well as those who remained negative throughout the study (including baseline).
- Annualized 6- to 12- month growth velocities and height SDS. These variables will be summarized separately for patients who were anti-GH antibody-positive at any post-baseline follow-up visit (negative at baseline) and those who were anti-GH antibody-negative at all visits (including baseline).

The difference between the annualized 6- and 12- month growth velocities will be presented separately for patients who were anti-GH antibody-positive at any post-baseline visit and those who were anti-GH antibody-negative at all visits (including baseline).

Graphic displays of the individual patient growth patterns (growth velocity); along with the longitudinal antibody profile over the course of the study will be prepared.

For the above analyses, if there is any patient who appears to have positive anti-GH antibody at baseline, they will be summarized separately from the other groups.

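### SAP 4.4.2 groups the 6-month growth velocity and Month 6 height SDS by antibody status through Month 12, so children who first test positive after Month 6 count as positive for growth completed while their samples were negative

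*SAP*

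**What the plan says.** Protocol 6.3.2 applies one antibody grouping to both velocities: "Annualized 6- and 12-month growth velocities and height SDS will be summarized separately for patients who were anti-GH antibody-positive at any post-baseline follow-up visit", against patients negative at all visits including baseline. SAP 4.4.2 keeps that split and adds that the positive group must have been negative at baseline: "who were anti-GH antibody-positive at any post-baseline follow-up visit (negative at baseline"). Patients positive at baseline are shown separately. The SAP then says: "The difference between the annualized 6- and 12- month growth velocities will be presented separately for patients who were anti-GH antibody-positive at any post-baseline visit", again against the always-negative group.

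Three other provisions matter here.

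- **Velocity definition.** SAP 4.4.2 bases growth response on "annualized growth velocity defined as (height - baseline height)/ (date of height assessment – date of baseline)*365.25 at any post-baseline visit". It is cumulative from baseline, not interval growth.
- **Sampling times.** Protocol 4.3.2 lists them: "Blood samples scheduled after baseline (Months 1, 3, 6, 9, and Month 12 or early discontinuation"). Two scheduled samples come after the 6-month velocity is complete.
- **Visit-matched antibody status.** For growth attenuation, a yes/no status, SAP 4.4.2 says a cross tabulation "will be provided for each antibody assay at each visit (Month 6, 9, and12"). No such visit-specific grouping is given for velocity or height SDS. Timing for each child is visible only in plots and listings: "Graphic displays of the individual patient growth patterns (growth velocity); along with the longitudinal antibody profile over the course of the study will be prepared".

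**The concern.** The 6-month velocity and Month 6 height SDS are outcomes fixed at Month 6, but the group a child falls into can be decided by a sample taken three or six months later. Antibodies not detected until Month 9 or 12 are an unlikely cause of growth recorded before then. The positive group therefore mixes growth with antibodies present and growth without them, and the negative group loses children who were antibody-negative throughout the period being summarized.

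Protocol 3.3.3 says the study will look at whether variations in growth are associated with antibody development. With no hypothesis test planned (SAP 4), a reader will compare the two group summaries by eye. If the grouping blurs the Month 6 comparison, that table is less informative than the collected data allow.

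**Working it through.** **The plan's own figure.** The documents give no expected size, SD or precision for the velocity contrast. Their only precision figure is the Clopper-Pearson interval for the antibody-positive proportion (Protocol 6.1, SAP 2.3). For 25 of 50 it recomputes to 35.53% to 64.47%, as printed. It is used here only as the source of group sizes.

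**Inputs from the documents**
- N = 50 evaluable, with 50% or 20% antibody-positive: 25 or 10 ever-positive children (SAP 2.3).
- Antibody samples at Months 1, 3, 6, 9 and 12 (Protocol 4.3.2).
- Target days 90, 180, 270 and 360 for Months 3, 6, 9 and 12 (SAP Table 2).

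**Inputs not in the documents**
- f: share of ever-positives whose first positive sample comes after Month 6.
- D: true deficit in 6-month velocity among children positive by Month 6.
- d: difference between late converters and never-positive children in growth before conversion (negative means slower).

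**Step 1: contrast under the SAP grouping.** Let m be the mean 6-month velocity of never-positive children.
- Ever-positive mean = (1-f)(m - D) + f(m + d) = m - (1-f)D + f·d.
- Always-negative mean = m.
- Deficit shown = (1-f)D - f·d.

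**Step 2: late converters grow like never-positives (d = 0).** The deficit shown is (1-f)D.

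| f (assumed) | Contrast remaining |
|---|---|
| 0% | 1.00 D |
| 10% | 0.90 D |
| 20% | 0.80 D |
| 30% | 0.70 D |
| 50% | 0.50 D |

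If D = 0 there is nothing to dilute.

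**Step 3: late converters differ (d not 0).** The term -f·d can raise or lower the deficit shown. If late converters were already slower growers by more than D, the deficit shown would exceed D. The direction is not fixed.

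**Step 4: children affected, at an assumed f of 20%.**
- 50% positive: 0.20 × 25 = 5 children. The SAP compares 25 with 25; status through Month 6 compares 20 with 30.
- 20% positive: 0.20 × 10 = 2 children. The SAP compares 10 with 40; status through Month 6 compares 8 with 42.

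**Step 5: contrast with status through Month 6.** With d = 0, the late converters return to the negative group with mean m, so the expected contrast is the full D.

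**Step 6: what remains after regrouping.** On target days, with no missed samples:
- First positive at Month 6: last negative at Day 90, so 90/180 = 50% of the 6-month interval precedes it.
- First positive at Month 9: last negative at Day 180, so 180/360 = 50% of the 12-month interval precedes it.
- First positive at Month 12: last negative at Day 270, so 270/360 = 75% precedes it.

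Regrouping stops the Month 6 summary from using later antibody status. It does not remove all pre-conversion growth from either velocity.

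**The case against.** **The clinical-impact objective does not rest on this table.** Protocol 2 assesses it through functional growth attenuation, for which the SAP already plans visit-matched tables at Months 6, 9 and 12. Individual profiles and listings also show timing. This stands, and it limits the importance of the point. The plots and listings still give no group contrast for velocity or height SDS.

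**The protocol expects little early effect.** Protocol 3.3.3 describes antibody-related attenuation as a response in the first 3-6 months followed by decline, and says a functional effect is very rarely detected without a gene mutation. D at Month 6 may therefore be small. This stands: no deficit in cm/yr can be taken from the documents.

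**Fixed groups have a purpose.** The SAP presents the difference between the 6- and 12-month velocities by group. Read as a within-child change, that needs the same children in the same group at both times, and a late converter's 6-month value is then a useful pre-antibody reference. This stands, and it rules out replacing the fixed grouping altogether.

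**The SAP bullet speaks of 6- to 12-month velocities.** It could be read as the interval between those visits. The from-baseline definition, the next SAP paragraph and Protocol 6.3.2 all point to two separate values.

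**Another analysis may exist.** The SAP contents list shows a Section 4.4.4 whose text was not available for this check, so a supplementary analysis there cannot be excluded.

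**Stronger inferences.** A reader might infer that the grouping favours a finding of no clinical impact. The documents do not support that: the direction depends on f and on how late converters grow, and the main clinical-impact tables are matched by visit. A reader might also object that membership depends on length of follow-up. That is true of any cumulative status, including the 12-month one. Early leavers are asked for a final sample (Protocol 4.5.5), and the effect cannot be sized.

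**Conclusion.** The misclassification follows from the text: an outcome complete at Month 6 is grouped by antibody results that can come from Months 9 and 12. How much it matters is unknown. The contrast falls to (1-f) of its true size only if antibodies slow growth solely once present and late converters otherwise grow like never-positive children. On those assumptions f = 10-50% leaves 90-50% of the contrast. That range is illustrative, because the documents give no conversion times. With f = 0 nothing changes, and if late converters differ for other reasons the bias could go either way.

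The affected summaries are secondary and descriptive. The primary endpoint and the growth-attenuation tables by visit do not change. This is an inexpensive improvement, not a flaw that threatens the study's conclusions.

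**What to change.** In SAP 4.4.2, summarize Month 6 velocity and Month 6 height SDS by antibody status on samples up to and including Month 6. Positive means negative at baseline and positive on at least one of those samples. Negative means negative at baseline and on all of them. Continue to show baseline-positive children separately.

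Keep the protocol's fixed grouping for the 12-month values and for the within-child difference between 6- and 12-month velocities. Add a note that the 12-month cumulative velocity still includes growth before conversion.

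The cost is one SAP sentence, one derived flag and one extra table, all from data already collected. The Month 6 table will have fewer positives: at an assumed f of 20%, 20 instead of 25, or 8 instead of 10. The final analysis follows database lock and no interim is planned (SAP 2.4), so the rule can be written down before the analysis.

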4.4.3 Exploratory Endpoints

This section is not applicable.

4.5 PHARMACOKINETIC AND PHARMACODYNAMIC ANALYSES

This section is not applicable.

4.6 SAFETY ANALYSES

Safety analyses will be performed on the Safety population.

4.6.1 Exposure of Study Medication

Study medication is open label daily SC injections of Nutropin AQ v1.1 at a dose of up to 0.043 mg/kg/day (0.3 mg/kg/week) for 12 months. Dose adjustments may be made per investigator assessment at the Month 6 visit for changes in weight of at least \pm 2 kg from baseline or insulin growth factor-1 (IGF 1) levels, if measured.

The extent of exposure and compliance to study medication for each patient will be calculated as follows:

The extent of exposure to study medication (days) = (last study treatment date – date of initial dose) +1.

Compliance to study drug between visits = [1 - number of missed dose / (date of current visit – date of previous visit)] x 100%

The number and percentage of patients who complete study treatment or discontinue prematurely from study treatment will be summarized by reason for discontinuation of study medication. Descriptive statistics (mean, standard deviation, median, minimum, and maximum) of extent of exposure and compliance to study medication will be provided for all patients in the Safety Population.

Study medication administration data and compliance will also be presented in data listings.

4.6.2 Adverse Events

Verbatim descriptions of adverse events (AEs) will be mapped to Medical Dictionary for Regulatory Activities (MedDRA, version 20.1 or newer) preferred terms and System Organ Classes. The severity of AEs will be graded (1 - mild, 2 - moderate, 3 - severe, or 4 - life-threatening) according to Table 1 of the Protocol, and the relationship to study medication (yes vs. no) will be assessed by the investigator according to Table 2 of the Protocol.

All adverse events with an onset date on or after Day 1 of study medication until 28 days after the last dose of study medication will be summarized (with frequency and percentage) by System Organ Class (SOC), preferred term (PT) within SOC, and

Nutropin AQ (Somatropin [rDNA origin])—Genentech, Inc. 11/Statistical Analysis Plan ML29543 severity grade. In the adverse event summaries, a patient having the same event more than once will be counted only once for that event type. For adverse events of varying severity, the highest (worst) grade will be used in the summaries. Missing severity or relationship to study drug will not be imputed.

Summaries of the following adverse events will be provided:

- AEs by SOC and PT
- SAEs by SOC and PT
- AEs by SOC, PT and severity
- AEs by SOC, PT and relationship to study medication
- SAEs by SOC, PT and relationship
- AEs leading to permanently discontinued study medication by relationship to study medication
- Death and cause of death (listing)
- AEs possibly indicative of hypersensitivity by relationship to study medication

All adverse event data will be presented in data listings.

Adverse Event of Special Interest (AESI)

ASEIs will be summarized using the following preferred term and MedDRA codes.

MedDRA Preferred Terms	MedDRA codes from MedDRA v20.1
drug-induced liver injury: Drug-induced liver injury	10072268
suspected transmission of an infectious agent via product	10072754
transmission of an infectious agent via product	10072753

4.6.3 Laboratory Data

Individual serum drug concentration / GH concentration, immunogenicity (anti-GH antibody screening, neutralizing anti-GH antibody, and antibody binding capacity) assay results will be listed, sorted by patient and visit.

The GH concentration at each visit will be summarized for patients in modified ITT population who have serum blood sample assayed for study drug/GH concentration. Descriptive statistics will include the number of observations (n), mean, standard

Nutropin AQ (Somatropin [rDNA origin])—Genentech, Inc. 12/Statistical Analysis Plan ML29543

deviation, coefficient of variation, median, minimum, maximum, geometric mean, and geometric coefficient of variation.

The serum concentration-time profiles in semi-logarithmic (log/linear) scales, growth velocity time-profile and antibody status (anti-GH antibody, neutralizing anti-GH antibodies, antibody binding capacity) for individual patient will be presented.

Patients who became pregnant during the study will be listed with available pregnancy test results.

4.6.4 Vital Signs

Height, weight and their change from baseline values will be summarized in terms of mean, standard deviation, median, minimum, and maximum at each visit. The average of three measurements of height at each visit will be used for analysis and computation of the height SDS and growth velocity. The height and weight data will also be presented in a data listing.

4.6.5 **Previous and Concomitant Medications**

All verbatim terms for medications recorded in the case report form (CRF) will be coded by preferred term and an anatomic therapeutic class (ATC) term using International Nonproprietary Name (INN) drug terms and procedures. Concomitant medications and prior medications will be summarized separately, based on the safety population, with number (percentage) of patients in each ATC class and preferred drug name. Prior and concomitant medications will also be presented in data listings.

Prior and concomitant medications are defined as follows:

- Prior medication is defined as any medication with start date before the first day of study drug, or checked to be prior to first study drug administration date, or medication with start date missing.
- Concomitant medication/treatment is any medication/treatment with start date on or after the initial dosing of study treatment, whichever occurs first.
 Medication/treatment that started before the first dose and continued during the study treatment will also be counted as concomitant medication/treatment.

4.7 MISSING DATA

Missing data will not be imputed for efficacy outcome measures. All available assessments will be reported with associated number of observations. If a patient discontinues study medication before the end of the 1-year treatment period, their growth rate will be computed for the last 3-month interval visit and used in the calculation of mean growth for that time interval only.

Nutropin AQ (Somatropin [rDNA origin])—Genentech, Inc. 13/Statistical Analysis Plan ML29543

There are two criteria for defining growth attenuation: (1) initial growth response greater than pretreatment velocity followed by reduction in growth response to below the pretreatment velocity in the subsequent 6- to 12-month treatment period, or (2) reaching \leq 2 cm per year at any scheduled visit: Month 3, 6, 9, or 12.

For criteria (1), if the pretreatment velocity is missing then growth attenuation is missing. Otherwise,

- 1. If patient discontinued < month 3, the growth attenuation will be missing because the initial growth response cannot be determined for criteria (1).
- 2. If patient discontinued \geq month 3 and < month 6, then:
 - a. If the height on Month 3 is missing, the growth attenuation will be missing because the initial growth response cannot be determined.
 - b. If the height on Month 3 is non-missing, the initial growth response can be determined but the growth attenuation cannot be determined because there is no Month 6 visit to determine the reduction in growth response to below the pretreatment velocity.
- 3. If patient discontinued ≥ month 6, the growth attenuation will be calculated based on the original definition.

For safety analyses, incomplete onset dates for adverse events and concomitant medications will be imputed according to the following algorithm:

- If the day is missing, the 1st of the month will be used.
- If the day and month are missing, January 1st will be used.

In cases where the imputation of the start/onset date leads to adverse events or concomitant medications occurring before treatment start, the start date will be set to the treatment start date.

Incomplete end dates for non-ongoing adverse events or concomitant medications will be imputed according to the following algorithm:

- If the day is missing, the last day of the month will be used.
- If the day and month are missing, December 31st will be used.

In cases where the imputation of the end date leads to adverse events or concomitant medications ending after date of last contact, the end date will be set to the date of last contact.

Nutropin AQ (Somatropin [rDNA origin])—Genentech, Inc. 14/Statistical Analysis Plan ML29543

